## 3 OBJECTIVES AND ENDPOINT / OUTCOMES

| OBJECTIVES  | ENDPOINT / OUTCOMES   | JUSTIFICATION   |
|---|---|---|
| Primary   |   |   |
| To conduct a multi-site RCT of the ADRD Palliative Care (ADRD-PC) program of dementia-specific palliative and transitional care ( intervention arm ) vs publicly available educational material for dementia caregivers ( control arm ) to compare 60-day hospital transfers (hospitalization and | Number of emergency room visits + hospital admissions within 60 days after discharge from index hospitalization | Hospital transfers are common for persons with late-stage ADRD, and are burdensome and stressful for the person and their family caregivers. Evidence shows that some hospital transfers are avoidable because acute illness can be treated in lower intensity settings, OR because goals of care are more comfort-focused. |

| OBJECTIVES   | ENDPOINT / OUTCOMES   | JUSTIFICATION   |
|--|---|---|
| emergency room visits) for persons with late-stage ADRD ( primary outcome ).

Secondary |   |   |
| To compare patient-centered secondary outcomes between intervention and control arms                 | a) Palliative Care Domain Index
b) Symptom Management at End of Life in Dementia
c) Neuropsychiatric Inventory Questionnaire
d) Post-acute use of palliative care, hospice
e) NH transitions                      | Physical and neuropsychiatric symptom distress is common in late-stage ADRD, and worsens toward death. Post-acute access to palliative services can improve outcomes, while new nursing home transitions may be avoidable with added community-based services and supports. |
| To compare caregiver-centered secondary outcomes between intervention and control arms               | a) documented communication about prognosis and goal of care
b) shared-decision making about hospitalization and other major treatment decisions
c) Family Distress in Advanced Dementia scale
d) Zarit Burden scale | Family caregivers serve as surrogate decision-makers in late-stage ADRD. They experience poor quality communication in usual care. In addition, caregivers experience significant emotional strain relative to caregiving role.   |

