## 4.3 JUSTIFICATION FOR INTERVENTION

Our preliminary studies justify the proposed RCT. First, we have created novel and effective methods to find and recruit dyads in hospital. Second, ADRD-PC is feasible and acceptable to people with ADRD, caregivers and clinicians. Third, palliative care clinicians deliver the ADRD-PC program with high fidelity, ranging from 77% (two follow-up calls) to 93% (dementia-specific palliative care, standardized education). Fourth, we used best practices to optimize enrollment and retention. Fifth, pilot data support relevance of ADRD-PC to persons with GDS 5-7, as in our pilot trial all stages enrolled equally, had similar death rate, and all 60-day hospital transfers affected GDS 5-6. Sixth, results show ADRD-PC improves intermediate outcomes strongly linked to hospital transfers. Thus, the necessary next step to advance the science of dementia-specific palliative care is an adequately powered RCT of the ADRD-PC program to test efficacy to improve patient and caregiver centered outcomes.

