- 1) **Dementia-specific palliative care** will be delivered by hospital-based specialty interdisciplinary palliative care teams. Encounters will include a physician or advanced practice provider and at least one additional discipline (nurse, social worker, chaplain). Visits will continue until hospital discharge, and will be documented in the EHR with the ADRD-PC Note Template. Palliative care clinicians will address four domains. First, the palliative care team will promote caregivers' **prognostic understanding** of dementia stage and its trajectory, contextualizing the acute illness with information about ADRD. Second, the palliative care team will conduct ADRD-specific **symptom management** of pain, other physical and neuropsychiatric symptoms, and recommend treatment consistent with best practices for ADRD. Third, the palliative care team will facilitate **shared decision-making** with the caregiver. Discussions may include exploration of overall goals of care, and decision-making about potentially burdensome treatments of resuscitation, ventilator use, feeding tubes, antibiotics, or future hospitalizations. When clinically appropriate, consultation will also include completion of new advance directives such as a Physician Orders for Life Sustaining Treatment (POLST) or comparable portable order set to document decisions for current care plans. POLST or similar documentation is in all study states and enhances treatment matched to patient preferences across healthcare transitions. Fourth, the palliative care team will assess **transitional care needs for community support services**. They will support dyads with post-discharge follow-up calls and referral to community services. (see Transitional care).
- 2) **Standardized caregiver education** will be provided by the palliative care team. Clinicians will share and discuss the booklet Advanced Dementia: A Guide for Families, which addresses common concerns and treatment decisions. Clinicians will individualize its content, highlighting key content and providing counseling about its relevance for current or future caregiving and treatment decision-making.

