- 3) **Transitional care** will be provided by the palliative care team. Pre-discharge, the palliative care team will explore **adequacy of patient and caregiver support for practical, emotional and spiritual needs**. Based on needs, they will recommend **community-based support services**. Examples could include community palliative care, hospice, home health, specialty geriatric or dementia clinics, adult day care or Alzheimer caregiver support groups. Near discharge, a member of the palliative care team will create a templated Palliative Care Plan and provide copies to the primary or post-acute care provider (PACP) AND the family caregiver. This document will summarize recommendations in the four domains and provide contact information for the palliative care team for follow-up questions. Post-discharge, a designated palliative care team member – usually a social worker or nurse coordinator – will call the family caregiver within 72 hours and again within 2 weeks after discharge. These calls may also be facilitated by a site CRC. The purpose of these calls will be to support implementation of the Palliative Care Plan and access to post-acute

supportive services. Calls will also be used to solicit concerns, offer emotional support, and make recommendations to help the caregiver overcome barriers to services.

**Control condition:** Patient-family caregiver dyads randomized to the control arm will receive educational materials from the Alzheimer's Association, specifically designed for late-stage ADRD caregivers. The patient will receive usual hospital and post-acute care.

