#### 6.2 FIDELITY

##### 6.2.1 INTERVENTIONIST TRAINING AND TRACKING

Ensuring fidelity to the ADRD-PC will be the responsibility of all site-based investigators. Our approach is based on NIH Behavior Change Consortium standards, with elements relevant to study design, interventionist training and standard operating procedures, and tools to support delivery of the ADRD-PC intervention.

| Types of Fidelity                  | Procedures to Ensure Fidelity   | Fidelity Monitoring  |
|------------------------------------|---|--|
| Study Design                       | 
 
Intervention based on a well-defined protocol
 
Standardized tools and templates
 
   | 
 
Protocol review and version control supported by Palliative Care Research Cooperative group
 
  |
| Standardized Training and Delivery | 
 
Training of Site-PIs on study protocol and SOPs
 
Training of Site-CRCs on study protocol and SOPs
 
Training of PC clinicians to deliver ADRD-PC
 
Audio-recorded training modules for consistent re-training or for new personnel
 
ADRD-tools and templates
 
          | 
 
Training material review by Palliative Care Research Cooperative group
 
Completed training
 
Post-training evaluation for PC clinicians (threshold score 80%)
 
Delivery of tools and templates to all study sites
 
   |
| ADRD-PC Intervention Enactment     | 
 
Monthly conference calls (led by [name]) with site PC clinicians
 
Monthly conference calls (led by UNC Project Manager) with site CRCs and site PIs=Utilization of ADRD-PC Program with standardized content areas
 
Documentation of clinical encounters in site medical record
 
 | 
 
Site-CRC tracking of completion of 4 ADRD-PC components: a) PC encounter, b) caregiver education, c) delivery of PC Plan to caregiver and primary or post-acute care provider (PACP) , and d) completion of 2 transitional care calls.
 
Threshold score 80% of dyads with completion of 4 ADRD-PC components.
 
Site specific feedback when fidelity drops below threshold.
 
Review 10% random of deidentified ADRD-PC encounter notes to ensure adherence,
 
 |

|  |  |   |
|--|--|---|

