Analysis to Meet Aim 1: We will compare control and intervention arms on hospital transfers (primary outcome) during 60 days post-discharge. This count outcome is defined as the total number of emergency room visits plus hospital admissions per at-risk patient-days. We will use Poisson regression with empirical 'robust' standard errors allowing for overdispersion to compare the transfer rates between groups. We will use the length of follow-up as the offset variable, which means that patients who have data only from the 30-day interview will be included. The primary analysis will be based on the model with main effects for treatment group, study site, GDS Stage and patient and caregiver sex as biological variables. Evaluation of the treatment effect will be based on a Wald test. The covariate-adjusted treatment effect will be quantified as an incidence rate ratio (IRR) with a 95% confidence interval. Considering that over 60% of patients in the pilot study did not have any hospital transfers, we will conduct a sensitivity analysis for the treatment effect on 60-day hospital transfers with a marginalized zero-inflated Poisson (MZIP) model, which may modestly increase power. Secondary Poisson and MZIP analyses will compare study arms for 30-day hospital transfer rates. An exploratory analysis will be conducted to examine interactions of treatment group with study site, sex, race / ethnicity and GDS Stage, respectively, on 60-day hospital transfers. While the proposed study is powered to detect whether or not ADRD-PC is effective, a much larger study would be needed to have adequate power to detect differences by sex or GDS Stage and would be justifiable only after the completion of this initial trial. An interaction model will be used if an omnibus test for interactions is statistically significant at the 0.05 level. A second exploratory analysis will evaluate a dose-response effect of the intervention on the hospital transfer rate. A dose for patients receiving the intervention is defined as the number of key intervention components used in fidelity monitoring (range 0 to 4 with 0 for controls). The dose effect is the incremental benefit of adding a single component; its rescaling gives the per-protocol effect of the full intervention.

---

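### The exploratory dose-response slope is labelled a per-protocol effect, but dose is set after randomisation and partly inside the outcome window, so it can be biased either way

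*Combined protocol and SAP*

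**What the plan says.** Under Aim 1, Section 9.4.2 states: "A second exploratory analysis will evaluate a dose-response effect of the intervention on the hospital transfer rate". Dose is "the number of key intervention components used in fidelity monitoring (range 0 to 4 with 0 for controls"). The slope is read as the gain from one more component, and "its rescaling gives the per-protocol effect of the full intervention".

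Section 6.2.1 lists the four components: (a) a palliative care encounter, (b) caregiver education, (c) delivery of the Palliative Care Plan, and "d) completion of 2 transitional care calls". Under Transitional care in Section 6.1, a team member "will call the family caregiver within 72 hours and again within 2 weeks after discharge". The primary outcome in Section 3 is "Number of emergency room visits + hospital admissions within 60 days after discharge from index hospitalization". For the in-hospital part, Section 6.1 says "Visits will continue until hospital discharge". Section 6.3 places randomisation directly after the enrolment interview, so every component comes later.

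Section 9.4.2 does not give the covariates or offset of the dose model. It names no landmark, no instrument and no adjustment for predictors of receipt. The confounder procedure in Section 9.4.1 deals with baseline imbalance between arms and its influence on the treatment-group coefficient, not with who receives more components within the intervention arm.

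**The concern.** Randomisation protects the comparison of arms. It does not protect comparisons between intervention patients with dose 4 and those with dose 2 or 3, and the dose slope uses both. Two routes to bias follow from the plan's own definitions.

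- **Overlap with the outcome window.** The calls are completed, or not, during the first two weeks in which transfers are counted. If an early transfer or death stops a call, the event lowers the dose, and high dose then looks protective.
- **Selection into components (a) to (c).** These depend on contact during a stay of varying length. If sicker or longer-staying patients receive more of them, the slope leans toward harm. If they receive fewer, it leans toward benefit.

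The practical risk is greatest if the intention-to-treat result is null. A pre-specified figure on the primary endpoint, labelled the per-protocol effect of the full programme, could then be read as evidence of efficacy or of harm when it partly reflects who received the components.

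**Working it through.** **Plan's own figure first.** The plan gives no figure for the dose analysis, so the check starts from the primary-endpoint power in Table 3. With n = 180 per arm, rates 0.53 and 0.33, and SE = √(1/(n·r₀) + 1/(n·r₁)):

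- SE = √(1/95.4 + 1/59.4) = 0.165; |log(0.33/0.53)| = 0.474; power = Φ(0.474/0.165 − 1.96) = 0.82, as stated.
- For a difference of 0.25 (0.53 vs 0.28) the same formula gives 0.96, as stated.
- The overdispersed rows (0.81 and 0.60) imply a variance-to-mean ratio of (z_effect/(1.96 + z_power))² = 1.67 to 1.68. The simulations use 1.67.

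**Inputs from the documents.** 0.53 transfers per 60 days and n = 180 per arm (Section 9.2, Table 3); 9% deaths (Section 9.2); pilot fidelity "ranging from 77% (two follow-up calls) to 93% (dementia-specific palliative care, standardized education") (Section 4.3).

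**Assumptions not in the documents.** Gamma frailty; deaths uniform over follow-up; 93% receipt for component (c); the share of early events that block the calls; receipt of (a) to (c) by risk group. The dose model is taken as log E(Y) = α + β·dose + log(follow-up), with full-dose IRR = exp(4β) and robust standard errors. This is the likely reading of Section 9.4.2, which does not state it.

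Under these inputs 12.7% of patients have a transfer or death before day 14. Call completion is held at 77% whenever blocking is varied.

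**Results with no true effect** (large-sample IRR; one-sided false findings at n = 180 per arm, nominal 2.5%):

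| Scenario | Full-dose IRR | False finding |
|---|---|---|
| No link | 1.00 | 2.5% benefit |
| 25% of events before day 14 block the calls | 0.96 | 3.9% benefit |
| 50% block | 0.93 | 5.8% benefit |
| 100% block (upper limit) | 0.85 | 12.8% benefit |
| Only events in the first 3 days block | 0.97 | 3.5% benefit |
| Higher-risk half receives (a) to (c) at 97%, lower-risk half at 83% | 1.09 | 7.6% harm |
| The reverse | 0.91 | 6.8% benefit |

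The standard error of the log full-dose IRR is about 0.20. The upper-limit bias is log 0.85 = −0.16, or about 0.8 of a standard error. At n = 159 per arm, 50% and 100% blocking give 5.7% and 11.7% false benefit.

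**Other assumptions.** A second simulation used log-normal frailty (SD 0.8), much stronger selection into all four components, and a 70% chance that a transfer by day 14 stops the calls. With no true effect it gave 0.91 for the window overlap alone, 0.74 if frailer patients receive fewer components and 1.41 if they receive more. The intention-to-treat test rejected in 5.0% to 5.7% of trials throughout.

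**Randomisation-based alternative.** Take 4 × log(IRR by arm) / mean dose in the intervention arm. Expected mean dose is 3 × 0.93 + 0.77 = 3.56, so the multiplier is 4/3.56 = 1.12.

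- *No true effect:* 0.99 to 1.01 in every scenario of the table.
- *True IRR 0.62:* 0.61 to 0.64, against 0.58 to 0.67 for the dose slope.
- *True IRR 0.62 with the stronger selection:* log(0.705)/0.883 gives 0.67 if frailer patients receive less, and log(0.664)/0.758 gives 0.58 if they receive more. The dose slope gives 0.49 and 0.83. The rescaling is therefore an approximation, but much closer to the truth.
- *Precision:* SD of the log full-dose IRR about 0.22, against 0.20 for the dose slope.

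**The case against.** The strongest reply is that little depends on this analysis. It is the second of two exploratory analyses, intention-to-treat is primary, and no hypothesis or sample-size figure uses the dose slope. Many readers will take a per-protocol figure as a non-randomised comparison anyway. This limits the severity, but it does not make the sentence correct: the text gives the interpretation as fact, with no assumption attached.

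The blocking mechanism can also be doubted. The calls go to the caregiver, a readmission need not prevent one, and Sections 8.1 and 9.2 continue caregiver data collection after a death. This stands, and the 0.85 case is best seen as an upper limit. Two-sided error rises only to about 6% or 7% with a quarter or half of early events blocking. The selection rates are likewise assumed, and the wide gap between the two sets of simulations shows that the size is not established. The direction toward harm rests entirely on that selection.

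Site, GDS stage and sex may be meant to carry over from the primary model and would remove some confounding. The plan does not say so, and baseline covariates cannot remove the effect of an early transfer on call completion.

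Finally, the instrument needs assumptions of its own, and centring on 1 under the null is nearly automatic for a rescaled intention-to-treat estimate. The results at a true IRR of 0.62 partly answer this. The assumptions remain, so the instrument is offered as optional.

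**Conclusion.** The concern holds. As written, Section 9.4.2 gives the rescaled slope a causal meaning that it has only if component receipt is unrelated to transfer risk. Nothing in the plan secures that condition, and the timing of the calls works against it.

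The likely bias is modest under the pilot fidelity figures: a null full-dose IRR of about 0.93 to 0.97 for partial call blocking and 0.85 at the limit, with 0.91 or 1.09 for moderate selection. Stronger assumed selection gives 0.74 or 1.41. The sizes are illustrative, since no document gives blocking or selection rates. The absence of protection against bias does not depend on them. The intention-to-treat primary analysis, the secondary analyses and the sample size are unaffected. The wording should be changed, but the point does not threaten the trial's main conclusion.

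**What to change.** **Simplest:** delete the sentence that equates the rescaled slope with a per-protocol effect, and report the dose slope as a descriptive association between components received and transfers.

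**If a full-dose effect is wanted:** use randomised arm as the instrument for dose, in a structural mean or two-stage model. Four times the intention-to-treat log IRR divided by the mean intervention-arm dose, with a bootstrap interval, is an acceptable approximation under a log link. State its assumptions: assignment acts only through the counted components, and each component has an equal, log-additive effect. A 0 to 4 count does not capture repeated visits, so both deserve comment.

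**In either case:** state the dose model, including covariates and offset.

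**Cost:** about a sentence of plan wording and a little analysis time, with no new data. The instrument gives a somewhat wider interval (SD 0.22 against 0.20 at n = 180 per arm) and adds the assumptions above.

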#### 9.4.3 ANALYSIS OF THE SECONDARY ENDPOINT(S)

**Aim 2:** To compare patient-centered secondary outcomes between intervention and control arms: a) symptom treatment (Palliative Care Domain index); b) symptom control (Symptom Management at the End of Life in Dementia scale, Neuropsychiatric Inventory Questionnaire); c) post-acute use of palliative care or hospice; and d) transition to nursing home care.

Analysis to Meet Aim 2: We will compare study arms during 60 days post-discharge on the following outcomes:

2.a. Symptom treatment: This ordinal outcome is the summation of presence (=1) or absence (=0) of 10 domains of palliative care. We will treat it as a continuous variable due to a high variation observed in the pilot data. We will use Student's t-test to compare the mean difference between study arms unless violation of assumptions warrants the Mann-Whitney test. We will use a multiple linear regression model with main effects for treatment group, study site, GDS Stage and patient and caregiver sex as a biological variable.

2.b. Symptom control: We will use Symptom Management (SM-EOLD) scale to measure caregiver report of patients' uncontrolled symptom distress and Neuropsychiatric Inventory Questionnaire (NPI-Q) to measure caregiver report of patients' neuropsychiatric symptom distress. Linear mixed models with random intercepts for patients will be used with a time indicator (30 vs 60 days follow-up) with the above main effects.

2.c. Use of post-acute palliative care or hospice: This outcome will be defined by whether patients ever use hospice or outpatient palliative care during the time from discharge to 60 days follow-up. We will compare the proportions using Pearson's chi-square test. Logistic regression will be used for multivariable modeling with the same main effects as in Aim 2.a. Final estimates will be reported as covariate-adjusted odds ratios.

2.d. Transition to nursing home care: This outcome will be defined by whether patients transition to nursing home care during the time from discharge to 60 days follow-up. We will compare proportions using Pearson's chi-square test. Logistic regression will be used for multivariable modeling with the same main effects as in Aim 1. Final estimates will be reported as covariate-adjusted odds ratios.

**Aim 3:** To compare caregiver-centered secondary outcomes between intervention and control arms: a) communication about prognosis and goals of care; b) shared decision-making; and c) caregiver distress (Family Distress in Advanced Dementia scale, Zarit Burden interview).

Analysis to Meet Aim 3: For the dichotomous outcome variables pertaining to communication (hypothesis 3a) and shared decision-making (hypothesis 3b), Pearson's chi-square test will test for differences in proportions between study arms. We will use logistic regression for the multivariable modeling. Treatment effect estimates will be reported as adjusted odds ratios. To test hypothesis 3c, we will use Student's t-test for mean difference since the outcome, Family Distress in Advanced Dementia (FDAD), is continuous. Linear mixed models as described for Aim 2.b. above will be used to test treatment effects for 30-day and 60-day outcomes jointly.

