## 4.2 SCIENTIFIC RATIONALE FOR STUDY DESIGN

We conducted a pilot RCT, randomizing 62 dyads of hospitalized patients with GDS 5-7 ADRD and their family caregivers to the ADRD-PC program vs usual care with publicly available education material. While underpowered to show a difference in 60-day hospital transfers, we found marked differences in intermediate outcomes. Intervention dyads were more likely to have an active POLST advance directive (79% vs 30%,  $p<0.001$ ) and to make a decision to avoid future hospitalization (13% vs 0%,  $p=0.033$ ). With ADRD-PC, persons with late-stage ADRD had more palliative care domains addressed in their treatment plan (Palliative Care Domain index score 7.6 vs 2.7,  $p<0.001$ , range 0-10), and symptom management for dyspnea (77% vs 34%,  $p<0.001$ ), constipation (93% vs 25%,  $p<0.001$ ), depression (83% vs 25%,  $p<0.001$ ) and delirium (80% vs 19%,  $p<0.001$ ). Caregivers were more likely to discuss prognosis (90% vs 3%,  $p<0.001$ ) and goals of care (90% vs 25%,  $p<0.001$ ). Intervention dyads also increased use of post-discharge palliative care (21% vs 7%,  $p=0.124$ ) and hospice (25% vs 3%,  $p<0.019$ ). Results indicate the potential for ADRD-PC to improve patient and caregiver-centered outcomes, including hospital transfers.

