## 9 STATISTICAL CONSIDERATIONS

### 9.1 STATISTICAL HYPOTHESES

**Aim 1:** To conduct a multi-site RCT of the ADRD-PC program (**intervention arm**) vs publicly available educational material for dementia caregivers (**control arm**) to compare 60-day hospital transfers (hospitalization and emergency room visits) for persons with late-stage ADRD (**primary outcome**). **H1:** *60-day hospital transfers will be lower in the intervention vs. control arm.*

**Aim 2:** To compare patient-centered secondary outcomes between intervention and control arms: a) symptom treatment (Palliative Care Domain index); b) symptom control (Symptom Management at the End of Life in Dementia scale, Neuropsychiatric Inventory Questionnaire); c) post-acute use of community palliative care or hospice; and d) new nursing home transitions. *Patients in intervention vs. control arms will have better symptom treatment (H2a) and symptom control (H2b); increased use of community palliative care or hospice (H2c); and fewer new nursing home transitions at 60 days post-discharge (H2d).*

**Aim 3:** To compare caregiver-centered secondary outcomes between intervention and control arms: a) communication about prognosis and goals of care; b) shared decision-making; and c) caregiver distress (Family Distress in Advanced Dementia scale and Zarit scale). *Caregivers in intervention vs control arms will more often have documented communication about prognosis and goals of care (H3a); report more shared decision-making about hospitalization and treatments (H3b); and report less caregiver distress at 60-days post-discharge (H3c).*

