### 9.2 SAMPLE SIZE DETERMINATION

Based on prior ADRD research, we project 15% dropouts (death, withdrawal) equally distributed between groups; caregiver data collection is completed after deaths as in our prior ADRD

research. Total sample size for analysis of 60-day follow-up outcomes is thus n=360. All statistical tests will be 2-tailed with an overall 0.05 significance level for pre-specified analyses. Statistical power is based on a 2-sided alpha of 0.05 significant tests and using standard deviation estimates from our pilot study (**Table 3**).

Power calculations assume a “best guess” 15% dropout (death, withdrawal) rate based on prior ADRD research (n=180 per group at 60-day follow-up) and a “worst case” 25% dropout rate (n=159 per group). These rates consider 9% patient mortality and 92% caregiver retention rate in the pilot. In our pilot data, 0.52 is the lower bound of the 95% CI for the IRR comparing

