**Table 3: Power for Comparing Intervention and Control Arms Based upon the Study Design**

| Aim       | Measure                                   | Control | SD  | Difference | Power, 15% dropout | Power, 25% dropout |
|-----------|---|---------|-----|------------|--------------------|--------------------|
| 1  | 60-day hospital transfers (Poisson rate)  | 0.53    | --  | 0.25, 0.2  | 0.96, 0.82         | 0.95, 0.79         |
|           | 60-day hospital transfers (overdispersed) | 0.53    | --  | 0.25, 0.2  | 0.81, 0.60         | 0.76, 0.55         |
| 2a | PC Domain Index (0-10)                    | 2.7     | 1.7 | 5, 0.5     | >0.99, 0.80        | >0.99, 0.75        |
| 2b | 60-day hospice use (%)                    | 3%      | --  | 22%,8%     | >0.99, 0.85        | >0.99,0.80         |
| 2c | Symptom distress (SM-EOLD)                | 36.4    | 7.8 | 4, 2.3     | >0.99, 0.80        | >0.99, 0.75        |
| 2d | Transition to nursing home care (%)       | 33%     | --  | 30%,15%    | >0.99, 0.82        | >0.99, 0.78        |
| 3a | Discussion of dementia prognosis          | 3%      | --  | 87%, 8%    | >0.99, 0.85        | >0.99, 0.80        |
| 3a | Discussion of goals of care (%)           | 25%     | --  | 65%,14%    | >0.99, 0.82        | >0.99, 0.77        |
| 3b | Decision-making about hospitalization     | 0%      | --  | 13%, 4%    | >0.99, 0.78        | >0.99, 0.73        |
| 3b | Decision-making about treatments          | 6%      | --  | 47%, 9%    | >0.99, 0.80        | >0.99, 0.75        |
| 3c | Family Distress in Advanced Dementia      | 2.4     | 0.5 | 0.15, 0.1  | 0.81, 0.47         | 0.76, 0.43         |

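### Table 3 gives power for hospice use alone, but H2c tests hospice or palliative care; for the stated 8-point difference, power on pilot rates is 0.54 to 0.68, not 0.80 to 0.85

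*Combined protocol and SAP*

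**What the plan says.** The endpoint is a composite wherever it is defined. The Synopsis and section 9.1 (H2c) name community palliative care or hospice. Section 9.4.3, item 2.c, defines the outcome as "whether patients ever use hospice or outpatient palliative care during the time from discharge to 60 days follow-up" and compares the arms with Pearson's chi-square test.

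Table 3 in section 9.2 has no row for this composite. Its nearest row is "60-day hospice use", labelled 2b, with:
- a control rate of 3%;
- differences of 22 and 8 points;
- power above 0.99 and 0.85 at 15% dropout, and above 0.99 and 0.80 at 25% dropout.

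In section 9.1, H2b is symptom control. The Table 3 row labelled 2c is the SM-EOLD symptom scale, so the two labels are interchanged relative to the hypotheses.

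Section 4.2 gives the pilot results for both components: hospice 25% against 3%, and post-discharge palliative care 21% against 7% (intervention against control).

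The palliative care component is worded in more than one way. It is *community* in the Synopsis, section 9.1 and the interview list in section 8.1, *outpatient* in item 2.c, and unqualified in the Schedule of Activities and section 3. In the intervention arm, section 6.1 says that a palliative care team member "will call the family caregiver within 72 hours and again within 2 weeks after discharge".

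**The concern.** The hospice row takes both its 3% control rate and its 22-point difference from the pilot's hospice result. The pilot's palliative care result is not used, although that component is half of the endpoint. A composite cannot be rarer than its commoner component, so on the pilot figures 3% is not a possible control rate for H2c.

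This matters because Table 3 gives a second, smaller difference in each row to show what the trial could still detect. For a binary outcome in this range, a higher control rate means a larger variance, so the same absolute difference is harder to detect. A reader who looks up H2c finds 0.80 to 0.85 for 8 points, and that figure belongs to another outcome. The interchanged labels make the mismatch easier to miss.

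A smaller matter is that item 2.c does not say whether the program's own post-discharge calls count as palliative care use. They fall inside the 60-day window and occur in one arm only.

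**Working it through.** **Inputs**
- Group sizes: 180 per group at 15% dropout and 159 at 25% (section 9.2).
- Test level: "Statistical power is based on a 2-sided alpha of 0.05 significant tests" (section 9.2).
- Table 3: 3% control, 8-point difference.
- Pilot controls: 3% hospice, 7% palliative care (section 4.2).
- Pilot intervention arm: 25% hospice, 21% palliative care (section 4.2).

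**Formula** (two proportions, pooled variance under the null, n per group)

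power = Φ[(d − 1.96·SE0) / SE1], where SE0 = √(2·p̄(1−p̄)/n), SE1 = √((p1(1−p1) + p2(1−p2))/n), d = p2 − p1 and p̄ is the mean of p1 and p2.

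**Step 1: reproduce Table 3.** For 3% against 11% with n = 180:
- SE0 = √(2 × 0.07 × 0.93 / 180) = 0.0269
- SE1 = √((0.0291 + 0.0979) / 180) = 0.0266
- power = Φ[(0.08 − 0.0527) / 0.0266] = Φ(1.03) = 0.848

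With n = 159 the result is 0.801. Both match the stated 0.85 and 0.80. The unpooled version also matches (0.854 and 0.808). The row is arithmetically right for hospice.

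**Step 2: bound the composite control rate.**
- Full overlap (every hospice user also used palliative care): max(3%, 7%) = 7%.
- No overlap: 3% + 7% = 10%.

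The documents do not give the overlap.

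**Step 3: same 8-point difference, composite control rate.** For 7% against 15% with n = 180:
- SE0 = √(2 × 0.11 × 0.89 / 180) = 0.0330
- SE1 = √((0.0651 + 0.1275) / 180) = 0.0327
- power = Φ[(0.08 − 0.0646) / 0.0327] = Φ(0.47) = 0.681

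The other cases use the same formula:

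| Control vs intervention | n = 180 | n = 159 |
|---|---|---|
| 3% vs 11% (Table 3, hospice) | 0.848 | 0.801 |
| 7% vs 15% (full overlap) | 0.681 | 0.626 |
| 10% vs 18% (no overlap) | 0.590 | 0.538 |

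The shortfall runs from 0.848 − 0.681 = 0.167 to 0.801 − 0.538 = 0.263, or about 17 to 26 percentage points of power.

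**Step 4: difference needed to recover the stated power** (0.85 at n = 180, 0.80 at n = 159).
- 7% control: about 10.3 points at either size.
- 10% control: about 11.5 points (n = 180) or 11.4 points (n = 159).

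**Step 5: pilot-size effects.** The pilot components bound the composite in the intervention arm at 25% (full overlap) to 25% + 21% = 46% (no overlap). The smallest contrast they allow is therefore 10% against 25%, which has power 0.966 (n = 180) and 0.944 (n = 159). For 7% against 25% the figures are 0.997 and 0.994.

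**The case against.** The strongest reply is that the row claims no more than it delivers: it is labelled as hospice use and is correct for that. Holding the difference at 8 points while raising the control rate is also a choice. Adding the palliative care component can raise the intervention rate too, and at pilot-size effects the composite keeps ample power. This stands, and it limits the point. A reader might infer that H2c is underpowered, but step 5 shows that the documents do not support that. The reply does not rescue the smaller figure, because nothing else in Table 3 tells the reader what difference in the tested endpoint can be detected.

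The 7% to 10% range is itself soft. The pilot randomized 62 dyads. If the arms were about equal (31 each, an assumption), 7% is about two control patients (0.07 × 31 = 2.2) and 3% about one (0.03 × 31 = 0.9). The range should therefore appear in the plan as an assumption.

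A reader might also infer that the follow-up calls will inflate H2c in the intervention arm. The documents do not show this:
- The interview list and H2c both refer to community services.
- Section 6.1 lists community palliative care as a referral destination, separate from the team's calls.
- Section 4.3 reports 77% fidelity for two follow-up calls in the preliminary studies, while section 4.2 records post-discharge palliative care in only 21% of pilot intervention dyads. The calls do not appear to have been generally counted there.

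What remains is an undefined term. Item 2.c says *outpatient* without definition, the outcome is reported by caregivers, and no section excludes the calls. The documents give no misreporting rate, so no size of bias can be claimed.

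**Conclusion.** The point holds as a mismatch between Table 3 and the endpoint. The 0.85 and 0.80 belong to hospice alone. For the H2c composite, an 8-point difference has power of 0.59 to 0.68 at 180 per group and 0.54 to 0.63 at 159. The difference detectable at the stated power is about 10.3 to 11.5 points.

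These figures assume that the pilot control rates carry over, that overlap lies anywhere between full and none, and that the test is the unadjusted two-sided comparison at 0.05.

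The error is confined to the smaller detectable difference of a secondary endpoint. It does not touch the sample size, the primary outcome or the planned test. Whether the calls count is an ambiguity to close, separate from the power figure.

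**What to change.** 1. Keep the composite as the H2c endpoint. Replacing it with hospice alone would change a prespecified outcome to fit a planning row and would drop a component that the intervention targets.
2. Add a Table 3 row for the composite with a 7% to 10% control rate and the overlap assumption stated. Give either the difference detectable at the stated power (about 10.3 to 11.5 points) or the power for 8 points (0.59 to 0.68 and 0.54 to 0.63).
3. Keep the hospice row, marked as a component of H2c, and correct the 2b and 2c labels to match section 9.1.
4. In item 2.c, use the single term *community palliative care or hospice*, as in section 9.1, and state that the protocol's 72-hour and 2-week calls do not count as use. Confine the exclusion to those calls, so that a genuine outpatient visit with the same hospital's palliative care team is not discarded by accident.

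The cost is one table row, two labels, a sentence of definition and a less favourable planning figure. Sample size, data collection and analysis method are unchanged. Under the Statement of Compliance, the amendment needs IRB approval before it takes effect.
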